##### 8.1.4.3 Possible muscle and liver injury

For muscle injury, CK, hepatic, and renal function laboratory data will be integrated with myopathy signs and symptoms. For management of CK elevations  $> 3 \times$  ULN, refer to [Appendix E](#). For liver injury, laboratory data will be integrated with hepatic signs and symptoms. Alanine aminotransferase increases  $> 2 \times$  ULN with symptoms of hepatitis or  $> 3 \times$  ULN with or without symptoms of hepatitis will be evaluated and managed according to guidelines.

##### 8.1.4.4 Increased risk for pancreatitis (TG $\geq 2000$ mg/dL)

To prevent the risk for pancreatitis, lab alerts will be given for TG values  $\geq 2000$  mg/dL. A subject with a TG  $\geq 2000$  mg/dL should have a confirmatory TG value obtained within 1 week. As a first step, the subject should be immediately counseled and managed on their adherence to a heart-healthy diet, restricted alcohol intake and diabetic control. A follow-on TG value should be obtained 2 weeks later. If the TG remains  $\geq 2000$  mg/dL then the study medication should be stopped, and the subject should complete the ET visit and be instructed to begin TG-lowering rescue medication (fibrates and/or OMG-3 compounds).

## 8.2 Serious Adverse Events

An adverse event or adverse reaction is considered serious if, in the view of either the Investigator or Sponsor, it results in any of the following outcomes:

- Death;
- A life-threatening adverse event;

- NOTE: An adverse event or adverse reaction is considered “life-threatening” if, in view of either the Investigator or Sponsor, its occurrence places the subject at immediate risk of death. It does not include an event that, had it occurred in a more severe form, might have caused death.
- Requires hospitalization or prolongation of existing hospitalizations;
- NOTE: Any hospital admission with at least one overnight stay will be considered an inpatient hospitalization. An emergency room visit without hospital admission will not be recorded as a SAE under this criterion, nor will hospitalization for a procedure scheduled or planned before signing of informed consent. However, unexpected complications and/or prolongation of hospitalization that occur during elective surgery should be recorded as adverse events assessed for seriousness. Admission to the hospital for social or situational reasons (i.e., no place to stay, live too far away to come for hospital visits) will not be considered inpatient hospitalizations.
- A persistent or significant disability/incapacity or substantial disruption of the ability to conduct normal life functions;
- A congenital anomaly/birth defect; or
- An important medical event.
  - NOTE: Important medical events that may not result in death, be life-threatening, or require hospitalization may be considered an SAE when, based upon appropriate medical judgment, they may jeopardize the subject or subject and may require medical or surgical intervention to prevent one of the outcomes listed in this definition. Examples of such medical events include allergic bronchospasm requiring intensive treatment in an emergency room or at home, blood dyscrasias or convulsions that do not result in inpatient hospitalizations, or the development of drug dependency or drug abuse.

### **8.3        Serious Adverse Event Reporting**

All observed or volunteered SAEs regardless of treatment group or suspected causal relationship to the study drug will be reported as described below. If a SAE occurs, the Sponsor or designee is to be notified within 24 hours of awareness of the event by the Investigator or designee.

All SAEs and follow-up information must be reported to the Sponsor or designee within 1 business day or 24 hours of awareness of the event as required by your local requirements by emailing or faxing a completed SAE report form to the following:

Safety Contact Information: PI [REDACTED]

Facsimile: PI [REDACTED]

E-mail: PI [REDACTED]

In particular, if the SAE is fatal or life-threatening, notification to the Sponsor or designee must be made immediately, irrespective of the extent of available AE information.

This timeframe also applies to additional new information (follow-up) on previously forwarded SAE reports, initial and follow-up reporting of exposure in utero (EIU) cases, and any SAEs that the Investigator considers related to study drug occurring after the 30-day follow-up period.

The Investigator must continue to follow the subject as medically necessary until the SAE has subsided or until the condition becomes chronic in nature, stabilizes (in the case of persistent impairment), or the subject dies.

In the rare event that the Investigator does not become aware of the occurrence of a SAE immediately (eg, if an outpatient study subject initially seeks treatment elsewhere), the Investigator is to report the event within 24 hours after learning of it and document the time of their first awareness of the SAE.

#### **8.4      Pregnancy Reporting**

For investigational products within clinical studies, an Exposure In Utero occurs if:

- A female becomes, or is found to be pregnant after receiving the study drug (eg, after Study Day 1).

If a subject participating in the study becomes pregnant during their participation in the study or within 30 days of discontinuing study drug, the Investigator must report the pregnancy to **PI** Drug Safety within 24 hours of awareness on the Exposure In Utero form.

A subject becoming pregnant while on study drug will immediately be withdrawn from the study and early termination study procedures will be performed.

The Investigator will follow the subject until completion of the pregnancy or until pregnancy termination (ie, induced abortion) and notify **PI** Drug Safety of the pregnancy outcome. The Investigator will provide this information as a follow up to the initial EIU form. The reason(s) for an induced abortion should be specified. If the outcome of the pregnancy meets the criteria for immediate classification as an SAE (i.e., postpartum complication, spontaneous abortion, stillbirth, neonatal death, or congenital anomaly), the Investigator should follow the procedures for reporting SAE(s).

In the case of a live birth, the “normality” of the newborn can be assessed at the time of birth (ie, no minimum follow-up period of a presumably normal infant is required before an EIU form can be completed). The “normality” of an aborted fetus can be assessed by gross visual inspection, unless pre-abortion findings are suggestive of a congenital anomaly.

#### **8.5      Expedited Reporting**

The Sponsor will report all relevant information about suspected unexpected serious adverse reactions that are fatal or life-threatening as soon as possible to the Food and Drug Administration (FDA), applicable competent authorities in all the Member States concerned, and to the Central Ethics Committee, and in any case no later than 7 days after knowledge by the Sponsor of such a case, and that relevant follow-up information will subsequently be communicated within an additional 8 days.

All other suspected unexpected serious adverse reactions will be reported to the FDA, applicable competent authorities concerned, and to the Central Ethics Committee concerned as soon as possible, but within a maximum of 15 days of first knowledge by the Sponsor.

The Sponsor will also inform all Investigators as required.

Expedited reporting of suspected unexpected serious adverse reactions related to non-investigational medical products (NIMPs) used in this study (e.g., simvastatin, atorvastatin, rosuvastatin, and/or ezetimibe) will not be necessary. Listings of the cases related to these NIMPs will be included in the Development Safety Update Report.

## **8.6 Clinical Laboratory Evaluations**

Clinical laboratory evaluations will be collected at the visits shown in the Schedule of Procedures ([Appendix A](#)) and the data captured will be forwarded to the central laboratory for evaluation. Assessments that require a subject to fast will be defined as no food or caloric beverage for at least 10 hours prior to sample collection. Subjects will be permitted to have water, black tea or black coffee.

Central laboratory results will be provided to the sites, with the exception of the post-randomization lipid values. TG alert values with a risk mitigation plan is in place with the Central Laboratory ([Section 8.1.4.4 Increased risk for pancreatitis \[TG  \$\geq\$  2000 mg/dL\]](#)). Laboratory results that appear potentially spurious based on the Investigator's clinical assessment and review of the subject's medical history may be repeated for confirmation of the finding. Reassessments of non-qualifying screening labs must be reviewed and approved by the Medical Monitor prior to obtaining the new specimen. The clinical rationale for performing repeat testing of screening assessments should be thoroughly documented.

Standard clinical laboratory evaluations for safety chemistry, coagulation, and hematology will be conducted at all study visits and the Follow-up Visit (only for subjects who had an abnormal result at Week 12 [or the ET Visit, if applicable] or an ongoing treatment-related adverse event). Clinically significant abnormal creatinine results at Week 12 (or the ET Visit, if applicable) will also be followed-up 2 weeks ( $\pm 3$  days) after the last dose of study drug in addition to the 4 week ( $\pm 3$  days) Follow-up Visit. See [Appendix B](#) for a list of clinical laboratory analytes.

A full fasting lipid panel will be assessed at the Pre-Screening Visit, if applicable, and at all other study visits, including the Follow-up Visit. Fasting apolipoproteins and LDL-C (ultracentrifugation) will be assessed at Study Day 1, Week 10, Week 12, the Follow-Up Visit, and the ET Visit, if applicable. In addition to these lipid parameters, hsCRP, IL-6, SAA, and fibrinogen will also be measured at Study Day 1, Week 10, Week 12, and the ET Visit, if applicable. Finally, ANGPTL4, adiponectin and cystatin-C will be measured at Study Day 1 and Week 12 (or the ET Visit, if applicable).

A urine sample for urinalysis will be collected at the Pre-Screening Visit, if applicable, the Screening Visit, Study Day 1, Week 6, Week 12, the Follow-up Visit (only for subjects who had an abnormal result at Week 12 [or the ET Visit, if applicable] or an ongoing treatment-related adverse event), and the ET Visit, if applicable. Urine protein:creatinine ratio and albumin:creatinine ratio will be performed at the Screening Visit, Study Day 1, Week 6, Week

12, the Follow-up Visit (only for subjects who had an abnormal result at Week 12 [or the ET Visit, if applicable] or an ongoing treatment-related adverse event), and the ET Visit, if applicable. Urinary NGAL will be measured at Study Day 1, Week 6, Week 12, the Follow-up Visit (only for subjects who had an abnormal result at Week 12 [or the ET Visit, if applicable] or an ongoing treatment-related adverse event).

Tests for HBV, HCV, and HIV will be conducted at the subject's first study visit, either at the Pre-Screening Visit, if applicable, or the Screening Visit.

For women of child-bearing potential only, a serum pregnancy test will be conducted at the Screening Visit, Week 12, and the ET Visit, if applicable. A urine pregnancy test will be conducted at the Pre-Screening Visit, Study Day 1, Week 2, Week 6, and Week 10.

Thyroid-stimulating hormone will be measured at the subject's first study visit, either at the Pre-Screening Visit, if applicable, or the Screening Visit.

Fasting insulin levels and FPG will be measured at Study Day 1 and Week 12.

HbA1c will be measured at the subject's first study visit, either at the Pre-Screening Visit, if applicable, or the Screening Visit, Study Day 1 and Week 12.

The estimated blood volume for the full study is 625 mL.

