## 1 INTRODUCTION AND BACKGROUND INFORMATION

### 1.1 Background

Gemcabene calcium is the monocalcium salt of a dialkyl ether dicarboxylic acid having 2 terminal gem dimethyl carboxylate moieties. Gemcabene has a dual mechanism of action that involves: (1) enhancing the clearance of very-low density lipoprotein (VLDL); and (2) blocking the overall production of hepatic triglyceride (TG) and cholesterol synthesis.

Gemcabene enhances the clearance of VLDL by decreasing the production of messenger RNA (mRNA) of the *APOC3* gene, thereby decreasing the production of the apolipoprotein C-III (apoC-III) protein. This in turn unmasks ApoE which (1) enhances the clearance of the VLDL remnants via ApoE remnant receptors; (2) reduces the formation of low-density lipoprotein (LDL) particles; and (3) enhances lipoprotein lipase mediated TG lipolysis allowing increased delivery of fatty acids to muscle and adipose tissue.

Gemcabene may also block the overall production of hepatic TG and cholesterol. Given its structural similarities to long-chain fatty acid, gemcabene may act as an inhibitor of acetyl CoA-carboxylase (ACC), subsequently leading to a decrease in hepatic TG production. Gemcabene may also inhibit one or more enzymes in the cholesterol synthesis pathway leading to less cholesterol in the cell, thereby upregulating LDL receptors in the liver.

In inflammatory states, cytokines, such as interleukin-6 (IL-6) and interleukin 1-beta (IL1-b), activate nuclear hormone receptors (NHRs), such as C/EPB-b, C/EPB-d and nuclear factor kappa B (NF- $\kappa$ B), and lead them to bind to the C-reactive protein (CRP) promoter and increase CRP mRNA production. Based on preclinical studies, gemcabene may inhibit the interaction of these NHRs on the CRP promoter and therefore reduce CRP mRNA production.

Taken together, gemcabene's mechanism of action should lower the full range of atherogenic particles (VLDL, IDL, and LDL) resulting in decreases in atherogenic particle number (apoB), particle cholesterol (non-HDL-C) and TG (when elevated); with concomitant lowering of hsCRP.

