#### 2.2.2 Secondary Efficacy Endpoints

The secondary endpoints are as follows:

- Change and percent change from baseline to Weeks 2, 6, 10 and 12 in fasting serum TG, and change from baseline to EOS in fasting serum TG;

- Change and percent change from baseline to Weeks 2, 6, 10, 12 and EOS in total cholesterol (TC), non-high-density lipoprotein cholesterol (non-HDL-C), HDL-C, and VLDL-C;
- Change and percent change from baseline to Weeks 10, 12 and EOS in Apo B, ApoA-I, ApoA-II, ApoA-V, ApoC-II, ApoC-III, and ApoE;
- Change and percent change from baseline to Weeks 10, 12 and EOS in LDL-C (ultracentrifugation), LDL-TG, VLDL-TG, HDL-TG;
- Change and percent change from baseline to Week 12 in lipoprotein size and particle number (NMR), and ANGPTL4;
- Change and percent change from baseline to Weeks 10, 12 and EOS in hsCRP, IL-6, serum amyloid A (SAA), and fibrinogen;
- Percent of subjects achieving a TG value < 500 mg/dL (5.65 mmol/L) at Weeks 10, 12, and EOS.

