#### 6.4.4 Visit T4 (Week 10)

The following procedures will be performed at Visit T4 (Week 10/Day 71 ±3 days):

- Perform symptom directed physical examination;
- Record vital signs and weight;
- Perform urine pregnancy test (for women of child-bearing potential only);
- Obtain blood sample for the following:
  - Safety chemistry panel, coagulation, and hematology;
  - Fasting lipid panel, LDL-C ultracentrifugation, apolipoproteins;
  - hsCRP, IL-6, SAA, and fibrinogen;
  - Reserve serum and PK plasma samples;

- Perform 12-lead ECG;
- Assess and document study drug compliance;
- Explain importance of continued adherence to a stable, heart-healthy diet and limited alcohol intake;
- Collect subject dose diary;
- Distribute subject dose diary;
- Assess adverse events and update concomitant medications; and
- Administer study drug (subjects will self-dose).

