## Efficacy Parameters

The following efficacy parameters will be assessed in this study:

Apo A-I	ApoA-II
ApoB	ApoC-II
ApoA-V	ApoC-III
Triglycerides	ApoE
High-density lipoprotein cholesterol	Low-density lipoprotein cholesterol
Non-high-density lipoprotein cholesterol	Very low-density lipoprotein cholesterol
SAA	Total cholesterol
High-sensitivity C-reactive protein	IL-6
ANGPTL4	Fibrinogen

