### 6.2.2 Secondary Endpoints

The secondary endpoints are as follows:

- Change and percent change from baseline to Weeks 2, 6, 10, and 12 in fasting serum TG, and change from baseline to EOS in fasting serum TG;
- Change and percent change from baseline to Weeks 2, 6, 10, 12, and EOS in total cholesterol (TC), non-high-density lipoprotein cholesterol (non-HDL-C), HDL-C, and very low-density lipoprotein cholesterol (VLDL-C);
- Change and percent change from baseline to Weeks 10, 12, and EOS in apolipoprotein (Apo) B, ApoA-I, ApoA-II, ApoC-II, ApoC-III, and ApoE;
- Change and percent change from baseline to Weeks 10, 12, and EOS in low-density lipoprotein cholesterol (LDL-C) (ultracentrifugation), low-density lipoprotein triglyceride (LDL-TG), VLDL-TG, HDL-TG;
- Change and percent change from baseline to Week 12 in lipoprotein size and particle number (NMR);
- Change and percent change from baseline to Weeks 10, 12, and EOS in hsCRP, IL-6, SAA, adiponectin, and fibrinogen; and
- Percent of subjects achieving a TG value < 500 mg/dL (5.65 mmol/L) at Weeks 10, 12, and EOS.
- Secondary endpoints related to safety include adverse events (AEs), safety laboratory parameters (chemistry including cystatin-C, hematology, coagulation values); urinalysis including urine protein:creatinine ratio, urine albumin:creatinine ratio and neutrophil gelatinase-associated lipocalin (NGAL); vital signs, electrocardiogram (ECG) results; and physical examinations (PEs).

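### The laboratory masking rule withholds only lipid values, so as written blinded sites receive post-randomization hsCRP, IL-6, SAA and fibrinogen results: a small, cheaply closed gap in the blind

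*Protocol*

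**What the plan says.** Protocol section 8.6 sets the release rule and gives one exception: "Central laboratory results will be provided to the sites, with the exception of the post-randomization lipid values". A separate arrangement covers TG alert values (section 8.1.4.4).

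The same section describes the lipid panel, apolipoproteins and ultracentrifugation LDL-C, and then continues: "In addition to these lipid parameters, hsCRP, IL-6, SAA, and fibrinogen will also be measured at Study Day 1, Week 10, Week 12", and at early termination (ET) if applicable. ANGPTL4 and adiponectin follow in their own sentence, at Day 1 and at Week 12 or ET.

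The four inflammatory markers are efficacy variables. Protocol section 2.2.2 lists "Change and percent change from baseline to Weeks 10, 12 and EOS in hsCRP, IL-6, serum amyloid A (SAA), and fibrinogen", SAP section 6.2.2 lists "Change and percent change from baseline to Weeks 10, 12, and EOS in hsCRP, IL-6, SAA, adiponectin, and fibrinogen", and Appendix B places hsCRP, IL-6, SAA, fibrinogen and ANGPTL4 under the statement "The following efficacy parameters will be assessed in this study".

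Protocol section 1.1 says the mechanism should lower atherogenic particles and TG, "with concomitant lowering of hsCRP". Section 5.3 commits to blinding the sponsor and all clinical site personnel.

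**The concern.** The usual reason to withhold post-randomization lipids from sites is that a drug-responsive value hints at the allocation. The protocol expects hsCRP to respond too, yet the written mask stops at lipids. A site holding the Day 1 and Week 10 values could form a view about a subject's arm while it is still meant to be blind.

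The judgements open to influence are those made by the investigator after the Week 10 result: causality of adverse events (section 8.1.3), whether a laboratory abnormality is clinically significant (section 8.1), and the handling of Week 12 findings and follow-up. Creatinine, CK and liver tests have to be returned for safety even if they also carry a hint. These four markers have no comparable role in the protocol.

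**Working it through.** **Are the markers outside the exception?** Section 8.6 refers back to the lipid panel, apolipoproteins and LDL-C as lipid parameters and introduces the four markers as additional to them. On that wording apolipoproteins are masked and the four markers are not.

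**Does any other section withhold them?** No. Sections 5.3 and 5.4 cover assignment and emergency unblinding. SAP section 4.1 covers unblinding after the last Week 12 visit and keeps the study team blind to individual subjects. Section 8.11 allows results of tests on study samples to be given on request, with no masking condition.

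**Does a specific safety rule need them?** No.
- Section 8.1.4 uses hemoglobin, renal measures, CK, liver tests and TG.
- Appendix E uses CK and liver tests.
- The Appendix B coagulation panel is PT, aPTT and INR, without fibrinogen.
- SAP Table 3 (potentially clinically significant values) contains none of the four.

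**When could a result reach a site?** The Week 2 and Week 6 visit lists (sections 6.4.2 and 6.4.3) have no draw. The first scheduled on-treatment draw is Week 10 (Day 71), where section 6.4.4 lists "hsCRP, IL-6, SAA, and fibrinogen". The Week 12 target is Day 85, so the window before the last TG sample is about 85 − 71 = 14 days, less laboratory turnaround. ANGPTL4 and adiponectin are drawn after randomization only at Week 12 or ET, so they could matter only for follow-up.

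**How much could hsCRP reveal?** The plan states no figure to reproduce, and the documents give no human hsCRP effect size. Assumptions:
- reduction r of 20% to 50% relative to placebo, the same in both active arms;
- log change normally distributed with SD 0.7;
- a rater who knows this whole model and uses hsCRP alone.

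Allocation is 1:1:1, so the prior chance of active drug is 2/3. With no marker, guessing active for every subject is right 66.7% of the time.

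Formulas, with Φ the standard normal distribution function:
- standardized shift: d = −ln(1 − r) / 0.7
- best cut-off, in SD units above the placebo mean change: c = ln(2)/d − d/2; guess active below it
- proportion correct: (2/3)·Φ(c + d) + (1/3)·[1 − Φ(c)]

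For r = 20%: d = 0.223/0.7 = 0.319 and c = 2.015. Proportion correct = (2/3)(0.9902) + (1/3)(0.0220) = 0.667. The gain is under 0.1 percentage point.

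For r = 50%: d = 0.693/0.7 = 0.990 and c = 0.205. Proportion correct = (2/3)(0.8840) + (1/3)(0.4188) = 0.729. The gain is 72.9 − 66.7 = 6.2 percentage points.

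A real investigator would do no better than this from hsCRP. About 90 subjects across 40 to 50 sites is 90/50 = 1.8 to 90/40 = 2.25 per site, too few to learn what a typical placebo change looks like.

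**The case against.** The strongest reply is that this is a wording gap with little behind it. Several parts of that reply stand.

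- **Release timing is not stated.** The documents do not say when these assays are reported or whether they are batched. A reader might infer that sites see Week 10 values before Week 12. The rule permits that, but nothing shows that it happens.
- **Scheduled diet counselling is not affected.** A reader might infer that a site that has guessed the arm would counsel differently and so shift TG. The last scheduled counselling is at Week 10, the visit at which the first on-treatment sample is drawn. Section 6.4.5 lists none at Week 12, and the dietary row in Appendix A ends at Week 10.
- **The primary endpoint is largely protected.** End of study TG averages Weeks 10 and 12. The Week 10 sample is drawn at the same visit as the first marker sample, and TG is measured centrally and withheld. Any effect would be indirect, through behaviour between Weeks 10 and 12.
- **Only hsCRP has a stated direction.** The supporting text on CRP is preclinical. No effect is claimed for IL-6, SAA or fibrinogen, so a strong clue from all four is not supported.
- **A coin toss is the wrong benchmark.** With two thirds of subjects on active drug, the comparison starts at 66.7%, not 50%.
- **Creatinine is an earlier clue.** Section 1.4 reports small mean increases within 2 to 4 weeks, and chemistry is returned at every visit. That clue is the price of safety monitoring and does not justify adding one that has no such purpose.

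What the reply does not remove is the text itself: efficacy biomarkers, one of them expected to respond, fall outside the only masking rule.

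**Conclusion.** The point holds as a minor one. As written, section 8.6 releases the Week 10 and Week 12 (or ET) hsCRP, IL-6, SAA and fibrinogen results to sites that are meant to be blind, and no specific safety rule calls for it.

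The gain in guessing active versus placebo is about 0 to 6 percentage points over 66.7%. That rests on the assumed 20-50% hsCRP reduction and SD of 0.7, and on hsCRP alone. It would be larger if the other markers also responded, which the documents do not claim, and nil before Week 12 if the assays are batched.

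The exposure is mainly to adverse event causality and laboratory-significance judgements after Week 10, including Week 12 and follow-up handling. The documents do not support a claim that the TG result is biased or that the blind is broken. The reason to act is that the repair costs almost nothing.

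**What to change.** Extend the exception in section 8.6 to cover post-randomization lipid values and post-randomization efficacy biomarkers (hsCRP, IL-6, SAA, fibrinogen and, at Week 12 or ET, ANGPTL4 and adiponectin), all withheld from sites until study unblinding. Because SAP section 4.1 starts group-level unblinding before follow-up ends, say that unblinding here means after the final database lock. If the assays are already batched, one sentence saying so achieves the same end.

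Apolipoproteins need no new wording, since 8.6 already treats them as lipid parameters. Release of safety chemistry, hematology, coagulation, urinalysis and the TG alert stays unchanged.

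The cost is one sentence in the protocol and a reporting flag at the central laboratory. The downside is that sites would not see these markers in real time and so could not follow up an abnormal value under the general rule for laboratory abnormalities in section 8.1.
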